7.7.3 Other Permitted Study Drug Adjustments

Standard dosing modifications will be made as described in Section 6.2.

For patients who are unable to tolerate the protocol-specified dosing schedule, dose adjustments are permitted, as described in Tables 3, 4, and 5, in order to keep the patient on study drug. In addition, if any surgery is planned, trial therapy should be interrupted one week prior to surgery and should be re-started as soon as possible after wound healing.

Dose modifications initiated by the site investigator (such as in response to a toxicity or safety lab level) will not require an everolimus PK level, unless the duration of the change lasts more than two weeks. If this was to occur, and a PK sample needed to be collected, the sample should be true trough. A true trough level is ~24 hours (+/- 4 hours) after the last dose was taken, and after 4 days of consistent dosing.

If treatment is interrupted due to toxicity, study drug should not be resumed until recovery to grade ≤ 1 is achieved. If recovery takes 6 weeks or more, the patient should be discontinued from the study. If recovery takes less than 6 weeks, study drug can be reintroduced at the initial dose or a lower dose level depending on the toxicity type and grade (see Tables 3 and 4). These changes must be recorded on the Dosage Administration Record and Dose Adjustment Log CRFs, as appropriate.

Dose adjustments (reduction, interruption, or possible dose re-escalation to starting dose) may also occur based on safety findings. All doses taken by the patient and all dose changes during the study must be recorded on the CRFs. Dose adjustments will also be made in the placebo group according to the placebo adjustment protocol.

7.7.4 Concomitant Medications

Patients must be instructed not to take any additional medications (over-the-counter, herbal, or other products) during the study without prior consultation with the investigator. All medications taken within 30 days of starting study treatment should be reported on the Concomitant Medications/Significant Non-Drug Therapies CRF. The following guidelines must be adhered to during the study:

- Investigational or commercial anti-proliferative agents other than study drug (including other mTOR inhibitors, e.g., sirolimus, temsirolimus) are prohibited.
- Co-administration with moderate or strong inhibitors of CYP3A4 (e.g., ketoconazole, itraconazole, ritonavir, erythromycin, fluconazole) or inhibitors of P-glycoprotein (PgP) must be avoided (refer to Table 9 and Table 10)
- Co-administration with strong inducers of CYP3A4, other than antiepileptics, must be avoided. Table 9 lists clinically relevant CYP3A inhibitors, inducers and the definition of strong and moderate inhibitors/inducers.
- Seville orange, star fruit, grapefruit and their juices affect P450 and PgP activity. Concomitant use should be avoided

Everolimus may affect the response to vaccinations making the response to the vaccination less effective. As everolimus is an immunosuppressant, live vaccines should be avoided while a patient is treated with everolimus.

Otherwise, the use of other concomitant medication/therapy deemed necessary for the care of the patient is allowed. The investigator should instruct the patient to notify the study site about any new medications he/she takes after the start of the study drug. All medications (other than study drug) and significant non-drug therapies (including physical therapy and blood transfusions) administered after the patient starts everolimus and for up to 84 days (12 weeks) after study drug discontinuation must be listed on the CRF.

A letter will be provided to each randomized patient's primary care physician outlining medications to avoid.

Table 9 Clinical relevant drug interaction: inducers and inhibitors of isoenzyme CYP3A

INDUCERS

Strong inducers:

avasimibe, carbamazepine, enzalutamide, mitotane, phenobarbital, phenytoin, rifabutin, rifampin (rifampicin), St. John's wort (*Hypericum perforatum*)

Moderate inducers:

bosentan, efavirenz, etravirine, genistein, lersivirine, lopinavir, modafinil, nafcillin, ritonavir, semagacestat, talviraline, thioridazine, tipranavir

Weak inducers:

amprenavir, aprepitant, armodafinil (R-modafinil), bexarotene, boceprevir, brivacetam, clobazam, danshen, dexamethasone, Echinacea, eslicarbazepine, garlic (*Allium sativum*), gingko (*Ginkgo biloba*), ginseng, glycyrrhizin, methylprednisolone, nevirapine, oxcarbazepine, pioglitazone, prednisone, pleconaril, primidone, quercetin, raltegravir, ritonavir, rufinamide, sorafenib, Stribild (combo of elvitegravir, cobicistat, emtricitabine, a tenofovir), sulfinpyrazone,telaprevir, terbinafine, ticagleror, ticlopidine, topiramate, troglitazone, vemurafenib, vicriviroc/ritonavir, vinblastine

INHIBITORS

Strong inhibitors:

boceprevir, clarithromycin, cobicistat, conivaptan, danoprevir/ritonavir, eltegravir/ritonavir, indinavir, indinavir, indinavir, itraconazole, ketoconazole, lopinavir/ritonavir, mibefradil, nefazodone, nelfinavir, posaconazole, ritonavir, saquinavir, saquinavir/ritonavir, telaprevir, telithromycin, tipranavir/ritonavir, troleandamycin, voriconazole

Moderate inhibitors:

Amprenavir, aprepitant, atazanavir, atazanavir/ritonavir, casopitant, cimetidine, ciprofloxacin, crizotinib, cyclosporine, darunavir, darunavir/ritonavir, diltiazem, dronedarone, erythromycin, fluconazole, fosamprenavir, grapefruit juice (*Citrus parasidi* fruit juice), imatinib, lomitapide, netupitant, nilotinib, *Schisandra sphenanthera*, tofisopam, verapamil

Weak inhibitors:

almorexant, alprazolam, alprazolam, amiodarone, amlodipine, amlodipine, atorvastatin, azithromycin, berberine, bicalutamide, bicalutamide, blueberry juice, cilostazol, cilostazol, cimetidine, clotrimazole, clozoxazone, cranberry juice, cyclosporine, delavirdine, everolimus, fluoxetine, fluvoxamine, fosaprepritant, ginkgo, goldenseal, isoniazid, isoniazid, ivacaftor, lacipidine, linagliptin, nilotinib, oral contraceptives, pazopanib, peppermint oil, propiverine, ranitidine, ranitidine, ranolaxine, ranolazine, resveratrol, roxithromycin, Seville orange, simeprevir, sitaxentan, tabimorelin, tacrolimus, teriflunomide, ticagrelor, tipranavir/ritonavir, tolvaptan, zileuton

Table 10 Clinical relevant drug interactions medicated by PgP

PgP Substrates	PgP Inhibitors	PgP Inducers
afatinib, alfuzosin, aliskiren, alogliptin, ambrisentan,	alogliptin, canaglifozin,	avasimibe,
apixaban, apremilast, aprepitant, atorvastatin acid,	cremophor RH40, curcumin,	carbamazepine,
atorvastatin, azithromycin, boceprevir, bosentan,	ketoconazole, lapatinib,	efavirenz, genistein,
carvedilol, caspofungin, ceritinib, cerivastatin,	lopinavir/ritonavir, mirabegron,	phenytoin,
citalopram, colchicine, CP-481,715, cyclosporine,	propafenone, simepravir,	quercetin, rifampin,
dabigatran, digoxin, docetaxel, domperidone,	valspodar, vandetanib,	St John's wort
doxepin, doxorubicin, eribulin, everolimus, fentanyl,	voclosporin	
fexofenadine, fidaxomicin, fluvastatin, fosamprenavir,		
atifloxacin, idelalisib, iloperidone, indacaterol,		
indinavir, irbesartan, lacosamide, lapatinib,		
levetiracetam, levofloxacin, linagliptin, linezolid,		
loperamide, losartan, maraviroc, mirabegron,		
moxifloxacin, naloxegol, nateglinide, nevirapine,		
nintedanib, lodaterol, paclitaxel, pantoprazole,		
paroxetine, pazopanib, phenytoin, posaconazole,		
pravastatin, proguanil, quinidine, quinine, ranolazine,		
riociguat, risperidone, ritonavir, rivaroxaban,		
saquinavir, silodosin, simeprevir, simvastatin,		
sirolimus, sitagliptin, sofosbuvir, sorafenib,		
tacrolimus, telaprevir, tenofovir, ticagrelor, tipranavir,		
tolvaptan, topotecan, umeclidinium, valsartan,		
vardenafil, vincristine, voclosporin, voriconazole		

Reference: Internal Clinical Pharmacology Drug-drug interaction (DDI) memo, updated April-2015 which summarizes DDI data from three sources including the FDA's "Guidance for Industry, Drug Interaction Studies," the University of Washington's Drug Interaction Database, and Indiana University School of Medicine's Drug Interaction Table.

7.7.5 Concomitant Medication Dose Adjustments

Samples for trough everolimus PK levels (drawn 0 to 2 hours before the next scheduled dose) will be taken two weeks (+/- one week) after the following events:

- 1. everolimus dose increase to a higher level than previously taken
- 2. reduction in the dose of a CYP3A4 or pGP inducer (e.g. reduction in anticonvulsant dose)
- 3. starting, or increasing the dose of, a CYP3A4 or pGP inhibitor

Trough is not required for dose re-escalation to a previously-used dose; or for dose decreases.

7.7.6 Study Drug Interruption or Discontinuation

An intent to treat approach will be used. All data acquired prior to termination for the reasons outlined below will be included in the primary analysis unless patient withdraws consent. Every effort will be made to conduct a final study visit with the participant and participants will be followed clinically until, if applicable, all adverse events resolve.

The term "interruption" refers to a patient stopping the study medication during the course of the study, but then re-starting it at a later time in the study (as determined by their study doctor).

The term "discontinuation" refers to a patient's premature and permanent withdrawal from the study treatment. The reason for discontinuation from treatment will be recorded. The patient may discontinue participation in the study for any of the following reasons:

- 1. adverse event(s)
- 2. abnormal laboratory value(s)
- 3. abnormal test procedure result(s)
- 4. protocol deviation
- 5. subject withdrew consent
- 6. Withdrawal by the investigator
- 7. lost to follow-up
- 8. administrative problems
- 9. intercurrent illness or event that precludes further visits to the study site or ability to evaluate disease (e.g.-mental status change, large pleural effusion).
- 10. death

If a patient has discontinued the study drug due to an unacceptable adverse event or an abnormal laboratory value, he/she should not have withdrawal of consent recorded as the reason for discontinuation. Instead, the reason for discontinuation must be recorded as due to adverse event or abnormal laboratory value.

All patients must have evaluations for 28 days after the last dose of study treatment. Participants that have ongoing adverse events at the 28 day follow-up visit will continue to be followed for an additional 8 weeks (56 days) to record any SAEs that are suspected to be related to study drug. Patients lost to follow up should be recorded as such on the CRF. Patients who discontinue study drug before completing the study should be scheduled for a visit as soon as possible, at which time all of the assessments listed for End of Treatment visit will be performed. At a minimum, all patients who discontinue study treatment, including those who refuse to return for a final visit, will be contacted for safety evaluations during the 28 days following the last dose of study drug. Patients will also be asked a series of neurocognition follow-up questions by phone and will complete the CBCL and DCDQ at the final follow-up call.

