2.1 Primary objective

To evaluate the safety of everolimus compared with placebo in patients with PTEN mutations focusing on NCI CTCAE Grade 3 and 4 adverse events, serious adverse events, and Grade 3 and 4 laboratory toxicities. The primary endpoint will be study drop-out rate due to side effects, comparing everolimus vs. placebo. Based on the published literature and our experience in prior TSC trials we hypothesize that the drop-out rate due to side effects in those receiving everolimus will be similar to those in the placebo group with minimal effect size (< 10% difference). We will also determine the frequency of adverse events by type and severity. We predict that the rate of adverse events will be no more than 10% higher in the everolimus group compared to placebo, but overall severity will be minimal.

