7.7.7 Withdrawal from the study and study evaluation completion

Patients may voluntarily withdraw from the study or be dropped from it at the discretion of the investigator at any time.

As a general rule, if a patient discontinues study drug and later is withdrawn from the study, the reasons for study evaluation completion may include the following:

- Protocol deviation
- Subject withdrew consent
- Lost to follow-up
- Death
- Use of non-study systemic anti-PTEN therapy
- Administrative problems

For patients who are lost to follow-up, the investigator should show due diligence by documenting in the source documents steps taken to contact the patient, e.g., dates of telephone calls, registered letters, etc.

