In objective 1, we will examine the safety and tolerability of everolimus by comparing the 1) dropout rates due to side effects, 2) dropout rates for any reason, and the 3) frequency of specific side effects in those receiving everolimus versus placebo. Based on the published literature and our experience in the tuberous sclerosis trial. we predict that the dropout rates due to side effects will be very similar across everolimus and placebo groups (<10% difference). However, we predict that everolimus will cause higher rates of medication-related side effects (≥10% difference) when compared to placebo. We will use chi-square statistics (or Fisher's exact test depending on cell counts) to compare dropout and rates of specific side effects. Statistical significance will be determined using a one-tailed test Type 1 error rate of α=.05, as only increases with everolimus treatment are expected. No false discovery rate correction will be applied because the concern is maximizing sensitivity to any increase in side effect prevalence with everolimus treatment. For dropout rates, we will also compute Kaplan-Meier survival analyses with discontinuation due to side effects or any reason as separate status endpoints. Number of days from baseline to medication discontinuation will be the time variable. Survival analyses are expected to be under-powered due to the generally low dropout rates expected, but these analyses can be useful for describing temporal trends. To ensure any observed group differences are not influenced by other variables or randomization imbalance, cox and logistic regression analysis will also be conducted with and without conditioning on relevant baseline covariates (e.g., demographics, language and cognitive ability, symptom severity).

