In objective 2, we will examine whether the everolimus group will show more improvement, compared to the placebo group, on the main neurocognitive efficacy composite outcome. Randomization Group (everolimus versus placebo) differences on the neurocognitive composite will be analyzed using mixed effects (growth curve) modeling, fully utilizing repeated measurements collected at three points (Time: baseline, 3-month follow-up, and 6-month follow-up). A significant interaction between Time and Randomization Group, with the everolimus group showing a more favorable outcome trajectory, will support the primary efficacy hypothesis. Maximum likelihood estimation will be implemented in the Mplus program version 7.2 or above.

Mixed effects (growth curve) model analyses will be conducted following the intention-to-treat principle. Data points that are missing due to subject attrition will be handled assuming that data are missing at random (MAR) conditional on observed information, which is less restrictive than missing completely at random (MCAR) assumed in fixed effects analyses such as ANCOVA and regression analysis. In this procedure, all available cases including the ones with missing information will be included in the analyses. By including every subject who completed at least one assessment, we are not only more likely to conserve power, but also less likely to produce biased effect estimates. In mixed effects analyses, the slope of the outcome will be modeled as the key

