17.1 Power Estimation

This is the first study to evaluate the efficacy of everolimus in patients with a PTEN mutation and ASD/DD. As such, analyses will be predominantly descriptive with the intent of generating plausible hypotheses to be tested in a Phase III confirmatory trial. The planned recruitment sample size of 40 was based on three considerations: 1) the expected recruitment potential of the three sites, 2) a desire to ensure sensitivity to any enrichment in side effects or problems with tolerability in everolimus treated patients, and 3) the need for adequate statistical power in examining primary and secondary efficacy outcomes. Assuming an overall dropout rate of approximately 10%, 44 patients will need to be enrolled to get 40 patients with complete trial data. However, following intent to treat procedures, all patients who are randomized, dosed, and for whom baseline data is collected will be included in statistical analyses. Statistical power considerations for each aim/hypothesis are described below. Except for safety analyses, where only everolimus-treated patients would be expected to show enrichment of dropout or side effects, statistical power estimates are based on one-tailed significance tests with Type 1 error rate of α =.05.

Primary Objective- Safety. The planned sample size of 40 is underpowered to detect small differences in dropout rates or side effects between everolimus versus placebo-treated groups. Statistical power will only be adequate if at least a 35% difference in the proportion of dropout/side effects is observed (1- β ≥.81), assuming a one-tailed Type 1 error rate of α =.05. This is equivalent to 1/20 patients experiencing an adverse event/side effect in the placebo arm and 8/20 in the treated arm. Similarly, statistical power of survival analyses will only be fair (1- β ≥.57) if a hazard ratio of 7.5 is observed, equivalent to a 5% dropout rate in the placebo group versus a 30% dropout rate in the everolimus group. However, because the goal is to maintain sensitivity to any potential enrichment in dropout or side effects, any indicator showing a difference of 10% or greater will be considered a meaningful difference and will be reported.

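### Section 7.7.6 drops already collected data from the primary analysis when consent is withdrawn, against sections 17 and 17.1; the main bias falls on the any-reason drop-out comparison

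*Combined protocol and SAP*

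**What the plan says.** Section 7.7.6 opens with "An intent to treat approach will be used". The next sentence reads "All data acquired prior to termination for the reasons outlined below will be included in the primary analysis unless patient withdraws consent". Withdrawal of consent is then reason 5 in that section's own list of reasons for discontinuation.

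Two other places define who is analysed, and neither makes an exception for consent:

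- Section 17.1: "all patients who are randomized, dosed, and for whom baseline data is collected will be included in statistical analyses".
- Section 17, efficacy model: "By including every subject who completed at least one assessment", which the plan justifies by power and reduced bias.

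On endpoints, section 2.1 says "The primary endpoint will be study drop-out rate due to side effects, comparing everolimus vs. placebo". Section 17 lists three comparisons under objective 1: "1) dropout rates due to side effects, 2) dropout rates for any reason, and the 3) frequency of specific side effects". It adds Kaplan-Meier analyses with discontinuation due to side effects and for any reason as separate endpoints.

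Two further provisions matter. Section 7.7.6 ends with a recording rule: a patient who stopped for an unacceptable adverse event or abnormal laboratory value is one for whom "he/she should not have withdrawal of consent recorded as the reason for discontinuation". Section 7.7.7 describes an exit in two steps, "if a patient discontinues study drug and later is withdrawn from the study", and lists withdrawn consent among the reasons for the second step.

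**The concern.** The clause concerns data already acquired, so it cannot be read as only ending further collection. Followed as written, it takes patients out of the analysis because of something that happened after randomization and that tolerability may influence. In a trial that compares drop-out, the excluded patients are themselves drop-outs.

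Two analysts working from this plan could build different analysis sets. The choice could also be made with allocations known, because sections 4.3 and 7.6 break each patient's blind at Month 6 or early termination. With 20 patients per arm, one patient more or less can change what is reported.

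**Working it through.** **1. The plan's own figure.** Section 17.1 gives power of at least 0.81 for 1/20 v 8/20 at one-sided α = 0.05. Exact enumeration of the one-sided Fisher test with 20 per arm and true rates of 5% v 40% gives 0.808. The figure reproduces.

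**2. What the clause does to each comparison.**

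| Patient | Side-effect drop-out (primary) | Any-reason drop-out |
|---|---|---|
| Stops for an adverse event or laboratory value, does not withdraw consent | Event kept | Event kept |
| Stops for an adverse event or laboratory value, later withdraws consent (7.7.7) | Event and patient lost | Event and patient lost |
| Withdraws consent for another reason | Non-event lost, denominator shrinks | Event and patient lost |

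The Kaplan-Meier analyses follow the same pattern: a removed patient leaves the risk set and is not counted as an event.

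**3. Effect of one patient (assumed counts, 20 per arm, everolimus first).**

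- Event lost: 3/20 v 1/20 is 15.0% − 5.0% = 10.0 points, which meets the reporting threshold in section 17.1. With one everolimus drop-out removed it is 2/19 v 1/20, or 10.5% − 5.0% = 5.5 points, which does not.
- Event lost: 6/20 v 1/20 is 25.0 points, one-sided Fisher p = 0.046. With one removed it is 5/19 v 1/20, or 21.3 points, p = 0.080.
- Non-event lost (primary endpoint only): 3/20 v 1/20 becomes 3/19 v 1/20, or 15.8% − 5.0% = 10.8 points. The difference rises.

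**4. Any-reason drop-out over a range of removal shares.** Inputs: 20 per arm (40 randomized 1:1), the 10-point threshold of section 17.1, assumed true drop-out of 30% v 10%, and an assumed share q of drop-outs in each arm removed as consent withdrawals. The rate after removal is p(1 − q) / (1 − pq). The last column is the exact binomial probability that the observed difference is 10 points or more.

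| q | Everolimus | Placebo | Difference | P(observed ≥ 10 points) |
|---|---|---|---|---|
| 0 | 30.0% | 10.0% | 20.0 | 0.85 |
| 10% | 27.8% | 9.1% | 18.7 | 0.80 |
| 25% | 24.3% | 7.7% | 16.6 | 0.74 |
| 50% | 17.6% | 5.3% | 12.4 | 0.60 |

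If the share is 50% on everolimus and 25% on placebo, the probability is 0.51.

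**5. Efficacy.** If the clause is applied to the composite as well, a patient who withdraws consent after Month 3 loses baseline and Month 3 scores. The mixed model in section 17 is meant to use those scores under its missing-at-random assumption.

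**The case against.** The strongest reply is the recording rule at the end of section 7.7.6. The primary endpoint is drop-out due to side effects, and the rule keeps those stops from being filed as consent withdrawal. This stands, and it narrows the point considerably. It does not close it, because the rule governs the recorded reason and not whether the data are kept. A patient correctly coded as an adverse-event stop who later withdraws consent still meets the exclusion.

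A reader might infer more than the documents support:

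- *That the clause generally lowers the primary drop-out rate.* It does not. Removing patients who withdrew for other reasons shrinks the denominator and can raise the rate, as step 3 shows.
- *That the efficacy analysis ceases to be intention-to-treat.* This assumes section 7.7.6 overrides section 17. The clause speaks of the primary analysis, and efficacy is the secondary objective in section 2.2. The term is loose, however: the Introduction names neurocognition as a primary endpoint alongside safety, so the reach of the clause needs stating.
- *That adverse events are hidden.* Sections 13 and 15 provide for recording, reporting and committee review of adverse events, and the clause removes none of that.

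The clause also speaks of data and does not expressly remove the patient from the denominator. Section 17 counts discontinuation for any reason, so an analyst might still count the exit. That is a reason to settle the wording.

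The inputs to step 4 are generous. Rates of 30% v 10% average 20%, against the roughly 10% overall that section 17.1 expects, although the same section uses 30% on everolimus in its survival example. The study is described as exploratory and mainly descriptive, the 10-point threshold governs reporting only, and the any-reason analyses are planned whatever the difference. Finally, whether collected data may be kept depends on consent terms that were not available for review.

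**Conclusion.** Wrong as written. Section 7.7.6 contradicts sections 17 and 17.1, and its exception is at odds with the intent-to-treat statement directly before it. That conclusion rests on the text alone.

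The size depends on the comparison. For side-effect drop-out, events are lost only in the two-step exit, and other exclusions can move the rate upward. For any-reason drop-out and its Kaplan-Meier curve, every consent withdrawal is a lost event. There the chance of seeing a 10-point difference falls from 0.85 to between 0.80 and 0.60 under the assumed 30% v 10% rates and equal removal shares of 10% to 50%. The documents give no expected number of consent withdrawals, so these figures show sensitivity and are not a forecast. The loss of efficacy scores is conditional on the clause being applied to efficacy.

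**What to change.** Replace the clause in section 7.7.6 with wording such as:

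*Data collected up to the date consent is withdrawn are kept in all safety and efficacy analyses, to the extent the consent terms allow; withdrawal of consent stops further collection only. Every randomized, dosed patient stays in the drop-out denominator. A consent withdrawal counts as an any-reason drop-out, and as a side-effect drop-out if the recorded reason for stopping drug was an adverse event or abnormal laboratory value.*

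Then align sections 7.7.6, 17 and 17.1 on one analysis set for safety and one for efficacy. The cost is a short text amendment and a check of what the consent form says about keeping data already collected. No patients, visits or assessments are added.
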